### 4.2 Inclusion criteria

1. All patients operated for PSP
2. Age  $\geq$  16 years
3. Able to read and understand the Dutch language
4. Mentally able to provide informed consent
5. Patients should have a preoperative chest CT scan in order to exclude evident secondary pneumothorax. Previously made CT scans, within a time range of maximum 5 years, are accepted. The identification of blebs or bullae on CT scan is not defined as secondary pneumothorax.

### 4.3 Exclusion criteria

1. Previous ipsilateral thoracic surgery (except diagnostic thoracoscopy only) or ipsilateral thoracic radiotherapy
2. Underlying lung disease that provoked the pneumothorax (secondary pneumothorax): genetically proven Birt-Hogg-Dubé syndrome, periodic pneumothorax in female patients in reproductive age with known endometriosis (or known catamenial pneumothorax), pulmonary cystic fibrosis, active pneumonia, lung fibrosis, chronic obstructive pulmonary disease (COPD), pulmonary ipsilateral malignancy
3. Contra-indications for TEA (infection at skin site, increased intracranial pressure, non-correctable coagulopathy, sepsis and mechanical spine obstruction)
4. Patients chronically (>3 months) using opioids will be excluded since postoperative baseline opioid requirement will be higher and TEA remains the preferred technique for these patients
5. Allergic reactions to analgesics used in the study

The shortened LOS however is only acceptable in case recurrence rates are equal between the early and late chest tube removal groups (patients' perspective). Therefore, three interim analyses will be performed under supervision of a DSMB after 90, 180 and 270 patients who completed 30-day follow-up. When the incidence of recurrences after early chest tube removal exceeds the incidence after late tube removal by more than 9 cases, then early tube removal will no longer be applied and the study will continue with the two late tube removal subgroups, unless the DSMB advises otherwise. The maximum allowable skewness of 9 extra recurrences after early tube removal is based on the following considerations. First, pneumothorax is not directly life threatening and 9 recurrences extra give a modest maximum excess of 5.49% (9/164). Second, a higher excess incidence ( $\geq 10$ ) leads to a decrease in expected savings in LOS by well more than 20%, and undermines the economic benefit of early tube removal too much (164 early removals save 230 hospital days and  $\geq 10$  extra recurrences reduce this gain with a least 50 days).

#### **4.5 Feasibility of accrual**

During the preparation phase of this study (between January and August 2022), thoracic surgeons from all Dutch hospitals were informed about our project. We hosted several meetings with surgeons, pulmonologists and anesthesiologists to discuss the design of this study proposal. The 28 hospitals that confirmed participation checked their annual number of surgeries for PSP, corresponding to a total number of 484 patients per year. Assuming that 10% will not meet our other eligibility criteria (e.g. coagulation disorder, allergy to analgesia), 436 patients will be eligible. Based on previous multicenter studies by our research group (MEDIAStrial and OPtrial that had inclusion rates varying between 30-90%) we conservatively assume that at least 30% is willing to participate, corresponding to an inclusion rate of 131 patients per year. With an inclusion period of 3 years, we expect to include all required patients within the time schedule. After METC approval, local feasibility will be carried out in the participating hospitals. Prior trials have shown that local feasibility is time-consuming and arranging logistics for 28 hospitals can be challenging. Therefore, strategies will take place to initiate the first steps of local feasibility ahead of time as the process can differ per hospital. Extra personnel is budgeted to aid in this process. We do not expect all hospitals to start inclusion at the same time (starting February 2024) and we took this into account in our total inclusion rate. Further, it is important that all hospitals perform the same surgical technique. During the previous meetings, all hospitals agreed to perform either total pleurectomy or talcage. To improve uniformity in performing total pleurectomy a video of correct performance of total pleurectomy will be spread. For correct use of the Thopaz+ system, Medela, the organization which provides Thopaz+ systems, training of the personnel on interpretation of the digital chest tube drainage system. Lastly, it is crucial for the participating centers to be able to perform both analgesic techniques and an instruction

course will be offered by the research group. After each hospital has started inclusions, monitoring of the study and regular meetings will be held (2 months after starting inclusions and yearly) to capture and evaluate potential inclusion or execution problems of the protocol promptly. If inclusion problems arise, a careful evaluation of the cause will take place. A newsletter will be propagated to regularly inform participating hospitals. Our study website will also contain all study information, enabling stakeholders to access information efficiently and boost feasibility. Proper information tools (folder and a video) will be made in collaboration with patients. The study website as well as the Longfonds website will propagate the study information and the information video for patients. Our patient advisory board, the patient panel and Longfonds patients have reacted enthusiastically to our research proposal. Based on our latest meetings with our patient advisory board we believe there is preparedness from patients to participate.

## **5. TREATMENT OF SUBJECTS**

### **5.1 General considerations**

#### *Surgery*

All included patients will undergo surgical pleurodesis through VATS, in order to achieve coalescence of the parietal and visceral pleura and prevent recurrence of pneumothorax. Pleurodesis can be achieved by either VATS pleurectomy or VATS chemical pleurodesis with talc.

With VATS pleurectomy the entire parietal pleura will be removed from approximately 2-3cm anterior to the spine (dorsally) to the mediastinal pleura anteriorly. The diaphragm will be left untreated, as well as the pleura covering the region of the subclavian vessels in the thoracic outlet.

With VATS talcage, the entire pleural space will be sprayed with sterilized talc, using a talc dispenser until all parietal pleura is covered with talc. Mediastinal, diaphragmatic and apical pleura may be treated with talc as well.

Thus far, both mechanical and chemical pleurodesis have been shown to be effective to provide pleurodesis. Several systematic reviews on this topic were not able to demonstrate solid preferences to one technique over the other, since available literature is of low quality and with high heterogeneity (20–22). As the chosen technique depends on the local preference or doctrine within hospitals, we are able by post-hoc subgroup analysis (non-randomized, but by hospital policy) to evaluate possible differences (hypothesis generating).

If during surgery ruptured bullae are visible (generally in the apex of the lung), they will be removed with wedge resection of the lung parenchyma. In case intact bullae are present in

the affected lung, wedge resection of these bullae is at the discretion of the lung surgeon. Performing a wedge resection is generally depending on the magnitude of the presence of bullae. Thus far it remains unclear whether bullectomy of intact bullae is an efficient procedure to prevent recurrent pneumothorax. Post hoc analysis of all CT images, as well as the existence of bullae during surgery, may provide further details on the question as to whether or not (and in what instances) remove intact bullae (hypothesis generating).

At the end of the operation, full expansion of the entire lung should be visualized and assured by the surgeon.

#### *Preoperative analgesics*

All patients will receive paracetamol (acetaminophen) 1000 mg. Non-steroidal anti-inflammatory drugs (NSAIDs) are prohibited in order not to intervene with the desired coalescence and fibrosis of the pleural surfaces. All preoperative analgesics administered will be registered in the case report form (CRF).

#### *General anaesthesia*

For induction and maintenance of anaesthesia in-house protocols will be used with the exception of lidocaine or esketamine which will not be administered during general anaesthesia. All patients will receive 8 mg dexamethasone to reduce additional postoperative opioid requirements and aid in the prevention of postoperative nausea and vomiting. In addition, a 5HT3 receptor antagonist will be administered if necessary and additional anti-emetics based on risk factors and local protocols.

#### *Management postoperative chest X-ray*

All patients will receive a postoperative chest X-ray at least 4 hours after surgery or ultimately the morning of POD1. In case the chest X-ray shows:

1. complete lung expansion, the chest tube can be removed if all chest tube removal criteria are fulfilled (see paragraph 5.2 Usual care for chest tube management).
2. a remaining pneumothorax with a distance of <2cm between the lung and the thoracic wall at the level of the hilum, the Thopaz+ system will be installed to a vacuum pressure of -8 cm H2O and in case of a distance >2cm to a vacuum pressure of -15 cm H2O. A new chest X-ray will be made 4 hours later. If this X-ray shows:
  1. complete lung expansion and all other chest tube removal criteria are fulfilled, the chest tube can be removed.

2. still a pneumothorax with a distance between the lung and the thoracic wall at the level of the hilum the chest tube remains in place with the same vacuum pressure. The next day the X-ray will be repeated.
3. an apical pneumothorax, the Thopaz+ system will not be adjusted since the appearance of a residual apical space is normal after apical wedge resection or bullectomy. The chest tube can be removed if all chest tube removal criteria are fulfilled.

## 5.2 Usual care

Two separate interventions will be investigated, one regarding postoperative chest tube management and one regarding pain management.

### *Usual care for chest tube management*

Postoperatively, a chest tube will be left in place in order to remove redundant air and assure coalescence of the visceral pleura with the parietal part of the chest (either after talcage or pleurectomy). The thickness of the inserted chest tube will be left to in-house protocol since there is no evidence that a thicker drain is more painful (23). Common sizes are 16 – 24 French. The chest tube is connected to a Thopaz+ system (Medela inc.) and installed to a vacuum pressure of -2cm H2O. In case the participating hospital does not use the new Thopaz+ system a vacuum pressure of -5cm H2O is accepted. For usual care, the chest tube will be left in place during a fixed period of 3 postoperative days. The chest tube will be removed at the earliest at POD 3 in case the following criteria are met:

1. The patient is lucid and capable of sitting up straight in bed on his/her own
2. No air leakage indicated by the Thopaz+ system during at least 4 hours, or <15 mL/min air leakage during at least 6 hours
3. Postoperative X ray (performed at least 4 hours after surgery or ultimately performed the morning of POD1) demonstrating complete lung expansion at the level of the hilum.
4. Absence of bloody drainage by the Thopaz+ system

### *Usual care for pain management*

For usual care, a TEA catheter will be placed in the awake patient after local anaesthesia of the skin. After correct placement of the epidural catheter at the 4th or 5th intervertebral space, a local anaesthetic (ropivacaine, levobupivacaine or bupivacaine) will be started with an additional opioid to the epidural solution according to in-house protocols. Before surgery, the skin of the incision site will be injected with a local anaesthetic. In the nursing ward, patients are allowed to mobilize under supervision when the motor function and sensibility of the

extremities allows it. Placement of a urinary catheter will be left to in-house protocols, however placement will be registered in the CRF. A provisional stop of the administration of the epidural infusion is planned after 48 hours (on the second postoperative day). In case NRS pain scores are  $\geq 4$  despite additional pain medication, the TEA can stay in place and the epidural infusion is resumed after a bolus of 5 mL of the epidural infusion fluid. After administration of the epidural infusion bolus, the vital signs of the patient are controlled for at least 30 minutes. Subsequently, NRS pain scores will be assessed daily until pain management is sufficient and the TEA can be withdrawn, with a maximum of 4 days. If rescue attempts to the epidural anaesthesia fail to improve pain scores, opioids may be withdrawn from the epidural solution and oral or intravenous opioids will be supplied. In case an accidental spinal puncture during placement of the TEA catheter occurs, the patient is not considered eligible for the TEA technique. In this case, a single-shot PVB is placed instead (see *intervention for pain management*). In case the epidural catheter is accidentally removed or is not placed correctly, the patient will receive systemic analgesia. This is already routine in usual care.

### 5.3 Intervention

#### *Intervention for chest tube management*

In the intervention groups, the chest tube will be removed at the earliest at 4 hours postoperatively in case the following criteria are met:

5. The patient is lucid and capable of sitting up straight in bed on his/her own
6. No air leakage indicated by the Thopaz+ system during at least 4 hours, or <15 mL/min air leakage during at least 6 hours
7. Postoperative X ray (performed at least 4 hours after surgery or ultimately performed the morning of POD1) demonstrating complete lung expansion at the level of the hilum.
8. Absence of pure blood drainage by the Thopaz+ system

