## **Optimal postoperative chest tube and pain management in patients surgically treated for primary spontaneous pneumothorax; a randomized controlled trial.**

### **Summary**

**Rationale:** Guidelines lack high quality evidence on optimal postoperative chest tube and pain management after surgery for primary spontaneous pneumothorax (PSP). This results in great variability in postoperative care and length of hospital stay (LOS). Chest tube and pain management are prominent factors regarding enhanced recovery after thoracic surgery, and in standardised care they are crucial to improve quality of recovery and decrease LOS. We hypothesize that early chest tube removal accompanied by a single-shot paravertebral blockade (PVB) for analgesia is safe regarding pneumothorax recurrence and non-inferior regarding pain, but superior regarding LOS when compared to standard conservative treatment.

**Objective:** Our objective is to compare the efficacy of early chest tube removal combined with single-shot PVB versus standard treatment (chest tube for at least 3 days and thoracic epidural analgesia (TEA)) after surgery for PSP.

**Study design:** Multicentre four-arm randomized trial, 2x2 factorial design

**Study population:** Patients  $\geq 16$  years with PSP referred for surgery.

**Intervention:** 1) Early chest tube removal when the following postoperative criteria are met: no air leakage for at least 4 hours, complete lung expansion on postoperative X-ray, absence of bloody drainage. 2) Intraoperative single-shot PVB (level T2-T11) with a local anaesthetic for analgesia.

**Main study parameters/endpoints:** Recurrence of pneumothorax as safety measure, proportion of pain scores  $\geq 4$  on a numerical rating scale of 0-10, and LOS

**Nature and extent of the burden and risks associated with participation, benefit and group relatedness:** There will be negligible risks to participation since the intervention strategies are already in use in some Dutch centres and have been demonstrated feasible and safe in single centre studies. The additional burden for the participants will be the completion of questionnaires.

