### **8.3 Study procedures**

Preoperatively, during the process of informed consent, patients will be asked to complete a baseline QoR-15 questionnaire, QLQ-C30, EQ-5D health status, and baseline adjusted iMTA questionnaire. A preoperative CT-scan will be made to rule out possible secondary causes of pneumothorax in case a prior CT scan of the last 5 years is not available, which is standard of care.

The surgical procedures are described under paragraph 5 *'treatment of subjects'* and are part of standard general health care. In case of a pleurectomy, a total pleurectomy will be performed. In case of chemical pleurodesis, the entire pleural surface will be sprayed with talc. All procedures will be performed by VATS (either 1, 2 or 3 incisions). After surgery one postoperative chest tube will be placed mid-thoracic and a Thopaz system is used which is set at a threshold of -2cm H2O (or -5cm H2O). A chest X-ray will be performed ultimately 4 hours after surgery or in the morning of POD1 which is also part of routine postoperative care. In case all chest tube removal criteria are met (*see paragraph 5.2 'usual care' and 5.3 'interventions'*), the chest tube will be removed during expiration.

Regarding postoperative analgesia, the TEA catheter is placed preoperatively in awake patients and will be left in place for at least 2 days after surgery (*see paragraph 5.2 'usual care'*). Patients are allowed to mobilize under supervision when the motor function and sensibility are intact. The need for a urinary catheter will be in accordance with in house protocols of the participating hospital. In case of a single-shot PVB, patients will receive a single shot of 2-3 mL local analgesic in the paravertebral space per intercostal level from T2-

T11 (see paragraph 5.3 'interventions'), corresponding to a total volume of 20mL. The PVB will be placed perioperatively before performing pleurectomy. No urinary catheter or mobilisation restrictions are needed with single-shot PVB. Oral painkillers will include paracetamol, oxynorm and oxycontin. NSAIDs will not be allowed.

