#### **12.2.2 Quality Assurance**

##### *Chest tube management*

Through a joint educational program with the company providing the digital drainage systems (Medela inc.), personnel involved in the peri-operative care will be trained on interpretation of the digital chest tube drainage system (Thopaz+). Also, how to extract data from the Thopaz+ system will be explained. Regarding insertion and removal of the chest tube, all centres should adhere to local protocols. All participating centres should adhere to the studies chest tube removal criteria (*see paragraph 5.2 usual care and 5.3 intervention*). With this approach we expect all participating centres will properly apply the protocol regarding chest tube management.

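### The drainage criterion for chest tube removal is worded differently in the early and late arms, and the protocol contradicts itself on which wording governs the early arm

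*Protocol*

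**What the plan says.** Protocol section 5.2 governs the late arm: "The chest tube will be removed at the earliest at POD 3 in case the following criteria are met". Its fourth criterion is "Absence of bloody drainage by the Thopaz+ system". Section 5.3 gives the early arm a list of the same length, with removal possible from 4 hours after surgery. Its fourth criterion is "Absence of pure blood drainage by the Thopaz+ system".

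Four other places bear on which list applies:

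- The Summary describes early removal with "no air leakage for at least 4 hours, complete lung expansion on postoperative X-ray, absence of bloody drainage", which is the section 5.2 term for drainage.
- Section 5.1, on the postoperative X-ray, covers all patients and says that with complete expansion "the chest tube can be removed if all chest tube removal criteria are fulfilled (see paragraph 5.2 Usual care for chest tube management". It does not mention the 5.3 list.
- Section 8.3 refers to 5.2 and 5.3 together for the removal criteria.
- Section 12.2.2 does the same: "All participating centres should adhere to the studies chest tube removal criteria", again citing both.

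On the X-ray that gates removal, section 8.3 says "A chest X-ray will be performed ultimately 4 hours after surgery" and then allows the morning of POD1 as an alternative. Sections 5.1, 5.2 and 5.3 make 4 hours the earliest time and the morning of POD1 the latest.

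**The concern.** Sections 3 and 3.1 present the chest tube factor as early removal against removal after at least 3 days. They do not say that the arms also differ in what kind of drainage prevents removal. Read literally, a patient whose drainage is blood-stained but not pure blood may have the tube out under 5.3, but not under 5.2, the Summary or the cross-reference in 5.1. A centre treating such a patient in the early arm finds two answers in one document.

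The rule reaches a primary outcome. Section 8.1.1 makes absence of a chest tube a discharge criterion, so whatever delays removal can delay discharge and add to LOS. The trial is unblinded (section 8.2.3) and 28 hospitals confirmed participation (section 4.5), so an undefined term that differs between arms can be read differently from centre to centre. If the lists are followed as written, part of any difference in LOS or postoperative safety could come from the criterion and not from the time of removal, and the report would have no stated basis for describing it.

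**Working it through.** **Step 1. Set the criteria side by side.**

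| Item | Late arm, 5.2 | Early arm, 5.3 |
|---|---|---|
| Earliest removal | POD 3 | 4 hours after surgery |
| Lucid, able to sit up | same | same |
| Air leak limits | same | same |
| X-ray and lung expansion | same | same |
| Drainage that bars removal | bloody | pure blood |

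Apart from the declared difference in timing, only the drainage item differs. No reason is given.

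**Step 2. See which term each place supports for the early arm.**

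- Section 5.3: pure blood.
- Summary: bloody.
- Section 5.1: bloody, through its reference to 5.2.
- Sections 8.3 and 12.2.2: both lists, so they do not resolve the conflict.
- Section 8.2.4: speaks of the removal criteria as if there were one set, with 4 hours or POD 3 as the distinction.

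**Step 3. Reproduce the planned LOS comparison.** Inputs from section 4.4: difference 1.4 days, SD 4.5, two-sided alpha 0.05, power 80%.

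- Normal approximation: n = 2 × (1.96 + 0.84)² × 4.5² / 1.4² ≈ 162.2, so 163 per group.
- Two-sample t-test: 163.15, so 164 per group; power at 164 is 80.2%.
- Drop-out of 10%: 164 / 0.9 = 182.2, so 183 per group and 366 in total.

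The stated figures reproduce, and nothing in this point changes them.

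**Step 4. Illustrate the size.** The protocol gives neither the share of patients with blood-stained but not pure-blood drainage nor the delay it would cause. The values below are assumptions. The shift in one arm's mean LOS is share × delay, and its weight is shift / 1.4.

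| Assumed share | Delay 1 day | Delay 2 days |
|---|---|---|
| 5% | 0.05 day (4%) | 0.10 day (7%) |
| 10% | 0.10 day (7%) | 0.20 day (14%) |
| 20% | 0.20 day (14%) | 0.40 day (29%) |
| 30% | 0.30 day (21%) | 0.60 day (43%) |

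**Step 5. Allow for the epidural.** Section 5.6 makes discharge follow removal of both the tube and the epidural. The epidural stays at least 2 days (8.3), with a provisional stop at 48 hours (5.2). Allocation is 1:1:1:1 (8.2.1), so half of the early arm has an epidural. If, as an assumption, it fully absorbs a one-day delay in that half, the one-day column halves: 0.025 to 0.15 day, or about 2% to 11% of 1.4 days.

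**Step 6. X-ray timing.** Under 8.3 read literally, 4 hours is a latest time; under 5.1, 5.2 and 5.3 it is an earliest time. A film taken before 4 hours would satisfy the first and not the others. The wording is the same for both arms, so it creates no difference between them.

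**The case against.** The strongest reply is that this is a drafting slip. The Summary, the cross-reference in 5.1 and the single set of criteria implied by 8.2.4 all point to one shared drainage criterion, and the authors may have meant the two terms as equivalents. This stands as the likelier explanation. It does not remove the problem, because centres are told to follow 5.2 and 5.3, and those lists differ.

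A second reply is that the trial compares two removal policies, so a criterion belonging to one of them does not bias the randomised comparison. That is right as far as it goes: the comparison of policies would stay valid, and what changes is how the effect may be described. But the policy then has to be declared, and at present the Summary and section 5.3 describe it differently.

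A third reply concerns size and safety. The assumed shares have no source in the protocol, and the epidural holds back discharge in half of the early arm anyway. The primary safety outcome and the interim rule concern recurrent pneumothorax, and the protocol offers nothing that links blood-stained drainage to recurrence. All of this stands.

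A reader might go further and infer that the early arm was deliberately given a looser rule, or that no LOS gain or safety signal could be credited to timing. The documents support neither. Intent is not stated, the terms are undefined, and in most of the illustrations the greater part of the 1.4-day planned effect is untouched by a wide margin.

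**Conclusion.** The inconsistency is certain: the two lists that centres must follow differ in one item, and the protocol gives conflicting criteria for the early arm. The consequence is conditional. Only if centres apply 5.2 and 5.3 literally does the early-versus-late comparison on LOS and safety include an undeclared difference in criterion alongside timing.

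The size cannot be derived from the documents. It is probably small, since the other three criteria are the same, only patients whose drainage falls between the two terms are affected, and the epidural limits the effect in half of the early arm. The figures above are illustrations on assumed inputs, not estimates, and the larger ones need both a high share and a two-day delay.

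It might also be inferred that both arms must share one criterion. The documents do not require that: a declared and defined difference would equally resolve the contradiction. The X-ray wording is a separate, minor inconsistency and adds nothing to a difference between arms.

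**What to change.** Reconcile the Summary and sections 5.1, 5.2 and 5.3 so that the drainage criterion for each arm is stated once, in the same words wherever it recurs, with the term defined. Make the cross-reference in 5.1 point to the list that applies to each arm. If a difference between arms is intended, declare it as part of the intervention. Which criterion applies is for the investigators to decide.

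Separately, reconcile the X-ray timing in section 8.3 with sections 5.1, 5.2 and 5.3.

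The cost is a wording amendment and a notice to the centres. The sample size and the randomisation do not change.
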